10.7 Safety Analysis

No formal inferential analysis is planned for the baseline and safety data, and only summary statistics will be provided.

10.7.1 Subject Assessment of Pain

Pain data will be summarized by treatment group using standard descriptive statistics (n, mean, standard deviation, median, first and third quartile, min, max) and using frequency and percentage (n, %) for each NRS score. Missing pain data will not be imputed. The Hodges-Lehmann estimator of the median difference in pain scores between treatment groups and the related 95% Moses distribution-free confidence interval will be presented by visit for descriptive purposes only.

10.7.2 Extent of Exposure

The number of complete and incomplete treatments per subject and the number of complete treatments per subject will be summarized using descriptive statistics (n, mean, standard deviation, median, first and third quartile, min and max) by treatment group and overall.

All treatment applications data will be listed.

10.7.3 Adverse Events Analysis

All Adverse Events (AEs) will be coded using MedDRA dictionary (version 22.0).

A treatment-emergent adverse event (TEAE) is defined as an adverse event that occurred, or worsened, on or after the date of the first application of study drug.

Statistical Analysis Plan

All treatment-emergent adverse events will be listed in a by-subject listing which will include both the term reported on the eCRF (verbatim term) and the MedDRA System Organ Class and Preferred Term. Relative start and stop days will be included along with the actual onset and resolution dates. Pre-treatment AEs will be listed separately.

If relationship to study drug/procedures is missing the closest relationship, i.e. “Related”, will be imputed. If severity is missing the greatest severity, i.e. “Severe”, will be imputed.

A summary table of TEAEs will be provided for each of the following in the safety population by treatment group and overall:

- Number and percentage (n, %) of subjects with any TEAE and frequency of TEAEs overall and by System Organ Class and Preferred Term;
- Number and percentage (n, %) of subjects with any TEAE and frequency of TEAEs, that occurred in >1% of subjects of the safety population, overall and by System Organ Class and Preferred Term;
- Number and percentage (n, %) of subjects with any AESI and frequency of AESIs overall and by System Organ Class and Preferred Term;
- Number and percentage (n, %) of subjects with any TEAE by closest relationship to study drug and frequency of TEAEs by closest relationship to study drug overall and by System Organ Class and Preferred Term;
- Number and percentage (n, %) of subjects with any TEAE by closest relationship to study procedures and frequency of TEAEs by closest relationship to study procedures overall and by System Organ Class and Preferred Term;
- Number and percentage (n, %) of subjects with any TEAE related to the study drug and frequency of TEAEs related to the study drug by System Organ Class and Preferred Term;
- Number and percentage (n, %) of subjects with any TEAE related to the study procedures and frequency of TEAEs related to the study procedures by System Organ Class and Preferred Term;
- Number and percentage (n, %) of subjects with any TEAE by greatest severity and frequency of TEAEs by greatest severity overall and by System Organ Class and Preferred Term;
- Number and percentage (n, %) of subjects with any TEAE leading to study discontinuation and frequency of TEAEs leading to study discontinuation overall and by System Organ Class and Preferred Term;
- Number and percentage (n, %) of subjects with any TEAE leading to study drug discontinuation and frequency of TEAEs leading to study drug discontinuation overall and by System Organ Class and Preferred Term.

The same summaries of TEAEs will be provided for the following subgroups: baseline AK grade (Grade 1 AK and Grade 2 AK), sex (Male and Female), number of baseline AK lesions (4-8 AK lesions and 9-12 AK lesions) and Fitzpatrick skin type (Type I, II and III and Type IV, V and VI).

A summary table of TEAEs will be provided for the following in the safety population by treatment group and overall:

- Number and percentage (n, %) of subjects with any TEAE and frequency of TEAEs, that occurred in >5% of subjects of the safety population, overall and by System Organ Class and Preferred Term.

A summary table of serious TEAEs will be provided for each of the following in the safety population by treatment group and overall:

- Number and percentage (n, %) of subjects with any Serious TEAE and frequency of Serious TEAEs overall and by System Organ Class and Preferred Term;
- Number and percentage (n, %) of subjects with any Serious TEAE by closest relationship to study drug and frequency of Serious TEAEs by closest relationship to study drug overall and by System Organ Class and Preferred Term;
- Number and percentage (n, %) of subjects with any Serious TEAE by closest relationship to study procedures and frequency of Serious TEAEs by closest relationship to study procedures overall and by System Organ Class and Preferred Term;

Statistical Analysis Plan

- Number and percentage (n, %) of subjects with any Serious TEAE related to the study drug and frequency of Serious TEAEs related to the study drug by System Organ Class and Preferred Term;
- Number and percentage (n, %) of subjects with any Serious TEAE related to the study procedures and frequency of Serious TEAEs related to the study procedures by System Organ Class and Preferred Term;
- Number and percentage (n, %) of subjects with any Serious TEAE leading to study discontinuation and frequency of Serious TEAEs leading to study discontinuation overall and by System Organ Class and Preferred Term;
- Number and percentage (n, %) of subjects with any Serious TEAE leading to study drug discontinuation and frequency of Serious TEAEs leading to study drug discontinuation overall and by System Organ Class and Preferred Term;
- Number and percentage (n, %) of subjects with any Serious TEAE leading to death and frequency of Serious TEAEs leading to death overall and by System Organ Class and Preferred Term.

In order to evaluate the impact of COVID-19 on the safety of the subjects, a summary table of TEAEs and serious TEAEs will be provided for each of the following for the safety population by treatment group and overall:

- Number and percentage (n, %) of subjects with any TEAE related to COVID-19 and frequency of TEAEs related to COVID-19 by System Organ Class and Preferred Term.
- Number and percentage (n, %) of subjects with any Serious TEAE related to COVID-19 and frequency of Serious TEAEs related to COVID-19 by System Organ Class and Preferred Term.

Listings of all AEs leading to death, all serious AEs, all TEAEs leading to study discontinuation, all AESIs and all AEs due to COVID-19 will be provided.

10.7.4 Physical Examination Analysis

Physical examination assessments will be summarized in terms of number and percentage (n, %) of subjects with 'Normal', 'Abnormal/Not Clinically Significant' and 'Abnormal/Clinically Significant' results for each body system.

Summaries will be presented by treatment group and overall at baseline and visit 6/ET.

A listing of all physical examination assessments will be provided.

10.7.5 Vital Signs Analysis

Descriptive statistics (n, mean, standard deviation, median, first and third quartile, min and max) by treatment group and overall will be presented for vital signs at baseline and visit 6/ET and for their change from baseline to visit 6/ET.

Number and percentage (n, %) of subjects with Clinically Significant Abnormal Values (as identified by the Investigator) and with Potentially Clinically Significant Values (see section 13.2) will be summarized by treatment group and overall at baseline and visit 6/ET.

A listing of all vital signs will be provided.

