10 STATISTICAL METHODS AND DATA CONSIDERATIONS

10.1 General Considerations

10.1.1 Baseline

For statistical analyses purpose, baseline is defined as the last measurement prior to the first DL-PDT treatment (regardless of treatment completion status).

Change from baseline and percent change from baseline will be calculated as:

Change from Baseline = PostBaseline Value – Baseline Value

$$\text{Percent Change from Baseline} = \begin{cases} \text{Baseline Value} \neq 0 \Rightarrow 100 \cdot \frac{\text{PostBaseline Value} - \text{Baseline Value}}{\text{Baseline Value}} \\ \text{Baseline Value} = 0 \Rightarrow \text{Missing} \end{cases}$$

Statistical Analysis Plan

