10.6.4.9 Analysis Visits Definition

Efficacy, safety and other variables will be summarized and analyzed by analysis visit. Analysis visit will be slotted according to the following table (see Table 9) to summarize the data by proper visit.

Table 9 - Analysis Visits Definition

Clinical Visit	Analysis Visit	Analysis Visit Number	Target Study Day
Visit 1	Baseline	1	1
Visit 2	Baseline	1	1
Visit 2b	Baseline	1	1
Visit 3	Week 1	2	8
Visit 4	Week 2-4	3	15
Visit 4b	Week 2-4	3	15
Visit 5	Week 3-5	4	22
Visit 6	Week 14/Final	5	99
Early Termination	Early Termination	6	---

Visit 2b and Visit 4b will occur only in case of incomplete treatment at Visit 2 and Visit 4 respectively. All efficacy assessments performed on Visits 2b and 4b will be assumed to fall at Visits 2 and 4 regardless of actual time.

Early termination visit assessments will be summarized as a separate visit in all by-visit outputs.

Unscheduled visits will be assigned to the same analysis visit of the last scheduled visit (including re-treatment visits) that occurred before the unscheduled visits.

All post-baseline safety assessments will be used for potentially clinically significant value (PCSV) determinations.

For efficacy and safety endpoints, if two or more assessments (include both scheduled and unscheduled assessments) are available for the analysis visits then all assessments will be listed and the following rules will be applied for determining the values to be used for the summary and analyses.

For efficacy endpoints:

Statistical Analysis Plan

- **Baseline Analysis Visit:** in presence of multiple assessments, the last assessment performed before the first DL-PDT treatment (regardless of treatment completion status) will be used for the summaries and analyses.
- **Week 2-4 Analysis Visit:** in presence of multiple assessments, the first assessment performed after the first DL-PDT will be used for the summaries and analyses.
- **Week 14/Final Analysis Visit (where applicable):** in presence of multiple assessments, the first assessment performed after the last DL-PDT will be used for the summaries and analyses.

For safety assessments:

- **Clinical Laboratory Evaluation:** in presence of multiple assessments on an analysis visit, the latest assessment will be used for the summaries and analyses.

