10.7.6 Clinical Laboratory Tests Analysis

Descriptive statistics (n, mean, standard deviation, median, first and third quartile, min and max) by treatment group and overall will be presented for blood chemistry, hematology and quantitative urinalysis parameters at baseline and visit 6/ET and for their change from baseline to visit 6/ET.

Statistical Analysis Plan

For summary purposes, laboratory values that are listed as above or below particular thresholds will be numerically imputed as above or below that threshold, respectively, by the minimum measured amount for that parameter. For example, if a parameter is measured to two decimal places, and has a result of "> 5" then, for summary purposes, the value of 5.01 will be used.

Number and percentage (n, %) of subjects for each response category of qualitative urinalysis parameter will be presented by treatment group and overall at baseline and visit 6/ET.

Number and percentage (n, %) of subjects with laboratory test values below, within and above the laboratory reference ranges will be summarized by treatment group and overall at baseline and visit 6/ET.

Number and percentage (n, %) of subjects with Clinically Significant Abnormal Values (as identified by the Investigator) and with Potentially Clinically Significant Values (see section 13.3) will be summarized by treatment group and overall at baseline and visit 6/ET.

Shift tables from baseline to visit 6/ET describing shifts to abnormality will be provided as well. Only subjects with a baseline result and a result at visit 6/ET for the parameter will be considered.

A listing of all clinical laboratory test will be provided.

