13.2 Potentially Clinically Significant Values of Vital Signs

Criteria for identifying vital signs values as Potentially Clinically Significant Values are the following.

Table 10 - Potentially Clinically Significant Values of Vital Signs

Parameter	Criteria		Change Relative to Baseline
Pulse Rate	≥ 120 beats/min	and an	increase ≥ 20 beats/min
	≤ 50 beats/min	and a	decrease ≥ 20 beats/min
Systolic Blood Pressure	≥ 160 mmHg	and an	increase ≥ 20 mmHg
	≤ 95 mmHg	and a	decrease ≥ 20 mmHg
Diastolic Blood Pressure	≥ 110 mmHg	and an	increase ≥ 10 mmHg
	≤ 45 mmHg	and a	decrease ≥ 10 mmHg
Body Temperature	$\geq 38.3^\circ\text{C}$	and an	increase $\geq 1.1^\circ\text{C}$
	$\geq 101^\circ\text{F}$	and an	increase $\geq 2^\circ\text{F}$

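### PCSV tables: the vital-sign count at baseline is zero by construction, some unscheduled values have no column or fall into Baseline, and the albumin SI limit is about 100 times below its g/L limit

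*SAP*

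**What the plan says.** - **Vital signs.** SAP 10.7.5 states that subjects "with Potentially Clinically Significant Values (see section 13.2) will be summarized by treatment group and overall at baseline and visit 6/ET". The criteria are in SAP 13.2, Table 10. Every row joins an absolute limit, by *and*, to an entry in the column headed "Change Relative to Baseline". For a high pulse rate that entry is "increase ≥ 20 beats/min".
- **Baseline.** In SAP 10.1.1, "baseline is defined as the last measurement prior to the first DL-PDT treatment (regardless of treatment completion status"), and the change is given by "Change from Baseline = PostBaseline Value – Baseline Value".
- **Laboratory tests.** SAP 10.7.6 uses the same two time points: subjects "with Potentially Clinically Significant Values (see section 13.3) will be summarized by treatment group and overall at baseline and visit 6/ET". The limits in SAP 13.3, Table 11, carry no change condition.
- **Which assessments count.** SAP 10.6.4.9 states: "All post-baseline safety assessments will be used for potentially clinically significant value (PCSV) determinations". It also states: "Unscheduled visits will be assigned to the same analysis visit of the last scheduled visit (including re-treatment visits) that occurred before the unscheduled visits".
- **Several values at one analysis visit.** The same section takes the latest value for laboratory tests and the value nearest the target date for vital signs. Only the efficacy rules restrict Baseline to pre-treatment values; the safety rules do not repeat that restriction.
- **Albumin.** Table 11 gives the limit as below 25 g/L under standard units and below 3.63 µmol/L under SI units.

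**The concern.** The PCSV counts are the rule-based safety screen that sits beside investigator judgement. They should show, by arm, how many subjects crossed a fixed limit.

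Three things looked wrong. A criterion that needs a change from baseline is tabulated at baseline. The rule on which assessments determine a PCSV is wider than the columns in which PCSVs are shown. One laboratory limit is printed as two values that are not equivalent.

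Unscheduled assessments matter here because both documents foresee them. SAP 6.2.5 and 6.2.6 allow laboratory tests and vital signs at any unscheduled visit. Protocol 8.6 ties such visits to retesting of abnormal laboratory results and follow-up of adverse events, which is where extreme values are most likely to be found.

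**Working it through.** **1. Vital signs at baseline.** The inputs are Table 10 and the definitions in SAP 10.1.1. At baseline the change is baseline minus baseline, which is 0. (Read strictly, the formula needs a post-baseline value, so the change is undefined and the criterion is still not met.)

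| Parameter | Change required | Is 0 enough? |
|---|---|---|
| Pulse rate, high or low | at least 20 beats/min | no |
| Systolic pressure, high or low | at least 20 mmHg | no |
| Diastolic pressure, high or low | at least 10 mmHg | no |
| Temperature, high | at least 1.1 °C (2 °F) | no |

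The baseline count is therefore 0 in both arms by construction. As an illustration, a subject with a systolic pressure of 170 mmHg before treatment exceeds the 160 mmHg limit but is not counted. The laboratory baseline column does work, because Table 11 has no change condition.

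**2. Unscheduled visits.** Combining the slotting rule with Table 9 of the SAP gives:

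| Last scheduled visit before it | Analysis visit assigned | PCSV column in 10.7.5 and 10.7.6? |
|---|---|---|
| Visit 2 or 2b | Baseline | yes, but the value is post-treatment |
| Visit 3 | Week 1 | no |
| Visit 4 or 4b | Week 2-4 | no |
| Visit 5 | Week 3-5 | no |
| Visit 6 | Week 14/Final | yes |

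The first row conflicts with 10.1.1, and the selection rules make the conflict live. For laboratory tests the latest value at an analysis visit is used, so a retest after Visit 2 would replace the screening value. For vital signs the value nearest Day 1 is used. Screening is 5 to 14 days before baseline (SAP Table 1), so a measurement fewer than 5 days after the first treatment is nearer to Day 1 than the screening value. If such a vital sign entered the Baseline column it could produce a non-zero count there, but that count would be a post-treatment event under the wrong label.

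**3. Albumin.** The formula is µmol/L = (g/L ÷ molar mass in g/mol) × 1,000,000. The documents give no molar mass for albumin; I assume 66,500 to 69,000 g/mol.

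- The plan's own figure is 3.63 µmol/L, and it is not reproduced.
- 25 ÷ 69,000 × 1,000,000 = 362 µmol/L, and 362.3 ÷ 3.63 = 99.8.
- 25 ÷ 66,500 × 1,000,000 = 376 µmol/L, and 375.9 ÷ 3.63 = 103.6.
- In reverse, 3.63 µmol/L is 0.24 g/L (66,500) to 0.25 g/L (69,000).
- The printed pair implies a molar mass of 25 ÷ 0.00000363 ≈ 6.89 million g/mol. With 363 in place of 3.63 it would be 25 ÷ 0.000363 ≈ 68,871 g/mol, inside the assumed range. This points to a factor-100 slip.
- Of the unit variants tried (25 g/L, 2.5 g/L, 25 mg/dL, 25 g/dL), only 25 mg/dL comes near the printed value, at 3.62 to 3.76 µmol/L.

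As a control, the 14 other mass-to-molar limits in Table 11 were converted in the same way, with assumed molar masses: urea, blood urea nitrogen, creatinine, uric acid (two limits), bilirubin, calcium (two), glucose (two), total cholesterol, LDL, HDL and triglycerides. For example, creatinine is 2.0 × 10 ÷ 113.12 = 0.1768 mmol/L, as printed. All agree with the printed SI values within about 0.5%. Albumin is the only outlier.

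**The case against.** The strongest reply is that these are drafting faults in descriptive output. SAP 10.7 plans no formal inference on safety data. All vital signs and laboratory values are listed. The baseline summaries show the maximum, so a high pre-treatment pressure is not hidden. The baseline column in 10.7.5 also serves the count of investigator-identified abnormal values, where it is meaningful. Clinically significant laboratory values and vital-sign changes after screening become adverse events (SAP 6.2.5, 6.2.6) and reach the adverse-event tables. Protocol 10.1.4.3 and 10.1.4.4 ask for PCSV counts by treatment group without confining them to two visits, so an any-post-baseline count already fits. The table shells are a separate document (SAP 13.1) and might settle the layout. The 25 g/L limit is usable, and the SAP does not say which column will be programmed.

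Most of this stands, and it bounds the point. It does not remove it: shells should implement the SAP, the SAP text disagrees with itself, and a listing does not replace a count by arm.

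Three stronger readings might be inferred, and the documents do not support them:

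- *Every vital-sign PCSV at Visit 6 will look new because baseline shows none.* Table 10 already requires an on-study change, so each such case is a real shift of at least the stated size.
- *All PCSVs at unscheduled visits are lost.* Those after Visit 6 have a column, those after Visit 2/2b are misplaced rather than missing, and the rest remain in the listings.
- *The PCSV tables fail as a whole.* Vital-sign PCSVs work at Visit 6, and laboratory PCSVs work at both time points apart from the albumin SI cell.

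**Conclusion.** The point holds, for descriptive safety tables only.

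- **Vital signs:** the baseline PCSV count is 0% in both arms whatever the data, given baseline as defined in SAP 10.1.1. The column is uninformative, and a reader could take it to mean that nobody had extreme values before treatment.
- **Unscheduled visits:** PCSVs after Visits 3, 4/4b and 5 have no table column, although 10.6.4.9 says they count. Post-treatment values after Visit 2/2b are assigned to Baseline, against 10.1.1. The number of subjects affected cannot be known from the documents.
- **Albumin:** the SI limit is 100 to 104 times lower than the g/L limit, assuming 66,500 to 69,000 g/mol. If the SI column is programmed, practically no subject would be flagged; if the g/L column is programmed, the error has no effect. The arithmetic shows that the two columns disagree, not which limit is intended.

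The primary and secondary efficacy analyses are unaffected.

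**What to change.** 1. In SAP 10.7.5, drop the baseline column for vital-sign PCSVs, or show there only the absolute limit and label it as such. Keep the baseline column for investigator-identified abnormal values.
2. In SAP 10.7.5 and 10.7.6, tabulate PCSVs by arm over any post-baseline assessment, scheduled or unscheduled, in line with 10.6.4.9.
3. In SAP 10.6.4.9, state that post-treatment values are excluded from Baseline for safety variables, so that the slotting and selection rules agree with 10.1.1.
4. In Table 11, reconcile the two albumin columns and state which column will be programmed. If 25 g/L is intended, the SI equivalent is about 363 µmol/L (362 to 376 over the assumed molar masses).

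The cost is a few lines in the SAP and matching edits to the table shells, which SAP 13.1 says will be finalised before database lock. No new data are needed.

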10.7.6 Clinical Laboratory Tests Analysis

Descriptive statistics (n, mean, standard deviation, median, first and third quartile, min and max) by treatment group and overall will be presented for blood chemistry, hematology and quantitative urinalysis parameters at baseline and visit 6/ET and for their change from baseline to visit 6/ET.

Statistical Analysis Plan

For summary purposes, laboratory values that are listed as above or below particular thresholds will be numerically imputed as above or below that threshold, respectively, by the minimum measured amount for that parameter. For example, if a parameter is measured to two decimal places, and has a result of "> 5" then, for summary purposes, the value of 5.01 will be used.

Number and percentage (n, %) of subjects for each response category of qualitative urinalysis parameter will be presented by treatment group and overall at baseline and visit 6/ET.

Number and percentage (n, %) of subjects with laboratory test values below, within and above the laboratory reference ranges will be summarized by treatment group and overall at baseline and visit 6/ET.

Number and percentage (n, %) of subjects with Clinically Significant Abnormal Values (as identified by the Investigator) and with Potentially Clinically Significant Values (see section 13.3) will be summarized by treatment group and overall at baseline and visit 6/ET.

Shift tables from baseline to visit 6/ET describing shifts to abnormality will be provided as well. Only subjects with a baseline result and a result at visit 6/ET for the parameter will be considered.

A listing of all clinical laboratory test will be provided.

